9.3.1 Patient Related Outcome Objectives

1. To evaluate longitudinal changes in symptom measures and determine the impact of the use of AEDs on these parameters.
2. To measure symptom burden over the course of the study period (one year) evaluate differences between patients individual symptom severity, overall mean symptom severity, and difference in scores on the interference items between those on placebo versus those on lacosamide.
3. To describe the variability of symptom severity longitudinally over the follow-up period.

9.3.2 Patient Related Outcome Methods

9.3.2.1 Patient Related Outcome Instruments:

The MDASI-BT will be utilized for this portion of the study. Full instruments are provided in the appendix. In addition, information regarding demographics and treatment history will be collected as part of the larger study and used in this analysis.

The MDASI-BT consists of 23 symptoms rated on an 11-point scale (0 to 10) to indicate the presence and severity of the symptom, with 0 being “not present” and 10 being “as bad as you can imagine.” Each symptom is rated at its worst in the last 24 hours. Symptoms included on the instrument include those commonly associated with cancer therapies, those associated with increased intracranial pressure, and those related to focal deficits. The questionnaires also include ratings of how much symptoms interfered with different aspects of a patient’s life in the last 24 hours. These interference items include: general activity, mood, work (includes both work outside the home and housework), relations with other people, walking, and enjoyment of

life. The interference items are also measured on 0 - 10 scales. The average time to complete these instruments is 5 minutes. The MDASI-BT has been translated into 18 languages [33, 34].

9.3.2.2 Patient Related Outcome Data collection:

After enrollment on the clinical trial, patients will complete as baseline measures the MDASI-BT. The patient will continue to complete the MDASI-BT at the time of clinical and seizure evaluation as long as the patient remains on the study, unless clinical deterioration makes self-report not possible before that time. The time when patients are unable to complete the self-report questionnaires will be used as part of the study analysis. The MDASI-BT will be completed only by the patient, unless changes in vision or weakness make this difficult. If this occurs, then the caregiver or research assistant may read the questions to the patient or assist with marking the severity number or score as described by the patient. A patient caregiver may complete the questionnaires as a patient-preference proxy if the patient's deficits preclude self-report. These reports will be used for descriptive purposes only. For the telephone interview, the research assistant will read the questions to the patient and mark the response indicated by the patient. If the patient rates any symptom as 7 or higher, the research assistant will instruct the patient to alert his or her physician team and the research assistant will also notify the clinical team that the symptom has been rated as severe by the patient. The forms will be reviewed by the principal investigator or research assistant for completion.

9.4 Electroencephalography (EEG)

EEGs will be reviewed in blinded fashion by [name] [name], PhD, a neurologist with fellowship training in clinical neurophysiology. He will evaluate background organization, presence of interictal epileptiform discharges (e.g., sharp waves, spikes), activity on the ictal/interictal continuum (e.g., periodic lateralized epileptiform discharges), subclinical seizures, and focal slow waves, particularly polymorphic delta waves.

10.0 CRITERIA FOR REMOVAL FROM TREATMENT

10.1 Criteria for Removal from Protocol Treatment:

- a. Completion of one year of therapy.
- b. Unacceptable toxicity (**see Section 6.1.3**).
- c. Seizure (as defined in Section 9.1).
- d. The patient may voluntarily withdraw from treatment at any time for any reason.
- e. Medical or psychiatric illness which in the investigator's judgment renders the patient incapable of further therapy.
- f. Pregnancy.

All reasons for discontinuation of treatment must be documented in the flow sheets.

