6.1.2 Supportive Care

- a. Dexamethasone should be used in the smallest dose to control symptoms of cerebral edema and mass effect, and discontinued if possible. Prednisone is not permitted because it induces CYP2C19.
- b. Febrile neutropenia may be managed according to the local institution's Infectious Disease guidelines. Measures may include appropriate laboratory testing, including blood and urine cultures and the institution of broad-spectrum antibiotics. If a source for the fever is not identified or the fever resolves when the neutrophil count recovers, antibiotics may be discontinued and the patient observed.
- c. The use of antiemetics will be left to the investigators' discretion.

d. Other Concomitant Medications

Therapies considered necessary for the wellbeing of the patient may be given at the discretion of the investigator. Other concomitant medications should be avoided except for analgesics, chronic treatments for concomitant medical conditions, or agents required for life-threatening medical problems. No other anti-convulsant medication are allowed while on the study. All concomitant medications must be recorded.

f. Surgery

If neurosurgical management is required for any reason, the procedure must be documented, including the indications for surgery, the surgical operative note and pathology report.

6.1.3 Definition of dose limiting toxicities (DLT):

Toxicities will be graded according to the NCI Common Terminology Criteria for Adverse Events (CTCAE) version 4.0. If multiple toxicities are seen, the presence of DLT should be based on the most severe toxicity experienced. DLT will be defined as any grade 3 toxicity that:

- Is not amenable to maximal medical management, and
- Is attributable to the study drug, and
- Occurs during treatment with lacosamide or placebo.

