6.2.1.2 Agent Administration

Lacosamide and placebo will be taken by mouth twice a day, at approximately the same times each day, spaced as close to 12 hours apart as possible. Medication may be taken with or without food. Missed doses should be taken so long as the dose will be taken within 6 hours of the scheduled time. Vomited doses will not be retaken unless the pill can be clearly identified in the vomitus. Patients will be given drug diaries every 3 months to monitor compliance (see Appendix 17.5).

6.2.1.3 Registration/Randomization:

See Section 15.3.2 for registration/randomization procedures.

6.2.1.4 Drug Dose/s and Treatment Schedule:

Patients may be taking peri-operative AEDs at the time of registration. These agents should be tapered off (on the investigator's preferred schedule) over 1-2 weeks. Lacosamide or placebo will be initiated at the same time that the taper commences. The starting dose of lacosamide or placebo will be 50 mg PO bid. Over 4 weeks, the dose should be increased to a target dose of 200 mg bid. A recommended scheme for dose escalation is to increase by 100 mg/day weekly until 200 mg bid is achieved. Deviations from this scheme that achieve a dose of 200 mg bid by 4 weeks will not be considered protocol violations.

6.3 Dose Modifications:

Patients who experience a treatment-related DLT as defined in Section 6.1.3 should have clinical evaluations and/or laboratory testing at appropriate intervals until the toxicity has resolved.

If a patient experiences DLT, the dose may be reduced or the treatment suspended, at the discretion of the treating investigator. Continuing therapy at a reduced dose should be seriously considered because of the risk of seizure associated with sudden cessation of any AED.

Doses between 50 mg bid and 200 mg bid are permissible during the study, and adjustments may be made as deemed appropriate by the investigator. However, every effort should be made to maintain the target dose of 200 mg bid whenever possible.

If a patient experiences DLT at a dose of 50 mg bid, the treatment should be discontinued.

Doses that are reduced for lacosamide or placebo-related toxicity may be re-escalated to the original dose level, if in the opinion of the treating investigator, it is safe to do so.

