Treatment may be held for up to 4 weeks, at the investigator's discretion. If the toxicity does not resolve to a level at which the investigator feels comfortable resuming study drug within 4 weeks, or if a patient experiences DLT at a dose of 50 mg bid, the treatment should be permanently discontinued.

For treatment or dose modification related questions, please contact the Study Chair or the MDACC OMCR at UT MDACC at [contact] or [contact].

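### Section 6.3 warns that stopping an AED abruptly can cause seizures, but no step-down of study drug is given when treatment ends, and only survival calls follow the one-year visit

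*Combined protocol and SAP*

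**What the plan says.** Section 10.1 lists the grounds for ending protocol treatment. They include "Completion of one year of therapy", "Unacceptable toxicity (see Section 6.1.3", seizure, voluntary withdrawal and pregnancy. The section asks only that the reason be documented.

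The toxicity ground points to Section 6.1.3, which is a definition ("DLT will be defined as any grade 3 toxicity that") and prescribes no action. The dosing rules are in Section 6.3:

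- On dose-limiting toxicity (DLT): "Continuing therapy at a reduced dose should be seriously considered because of the risk of seizure associated with sudden cessation of any AED".
- On the range: "Doses between 50 mg bid and 200 mg bid are permissible during the study".
- On interruption: "Treatment may be held for up to 4 weeks".
- DLT at 50 mg bid leads to discontinuation.

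For peri-operative AEDs, Section 6.2.1.4 does ask for a taper over 1-2 weeks: "These agents should be tapered off". For study drug the same section describes only the way up: "A recommended scheme for dose escalation is to increase by 100 mg/day weekly until 200 mg bid is achieved".

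Figure 8-1 places the last treatment visit on Day 1 of Month 13. Its footnotes put drug reorders after the telephone contacts of months 2, 5 and 8, and limit the four-weekly calls for symptoms and adverse events to the treatment period. The calendar then shows only survival calls.

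**The concern.** The protocol names abrupt AED withdrawal as a seizure hazard, tapers the AED that it removes at entry, and gives no way down from the one it may have given for a year at 400 mg/day. A site that follows the text literally can stop a patient from full dose in one step, and for one-year completers no scheduled contact afterwards asks about seizures.

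The main stake is patient safety. The second is the primary endpoint, time to first seizure. Only the lacosamide arm can have seizures caused by withdrawal of study drug, so among patients who stop before one year any such events would fall in that arm alone.

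**Working it through.** **1. What each way of stopping requires**

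| Reason treatment ends | Step-down stated? | Possible dose at the stop |
|---|---|---|
| One year completed, 10.1(a) | None | Up to 200 mg bid |
| Toxicity above 50 mg bid, 6.3 | Permitted, not required | Up to 200 mg bid |
| DLT at 50 mg bid, 6.3 | Already at the lowest dose | 50 mg bid |
| Voluntary withdrawal, 10.1(d) | None | Up to 200 mg bid |

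Supply points the same way. The three reorders precede the visits of months 4, 7 and 10, and none precedes the last visit. The pill-count form in Appendix 17.4 tells staff not to hand leftover tablets back.

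**2. Speed of an abrupt stop.** Section 2.5 gives a half-life of about 13 hours. Five half-lives are 5 × 13 = 65 hours (2.7 days), when 0.5^5 = 3.1% of the drug remains. The recommended titration run in reverse (300, 200, 100 mg/day, one week each) takes three weeks.

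**3. How many stop.** Inputs are 151 per arm, an 8% one-year lacosamide seizure risk and 15% loss (Section 11.1), and discontinuation for adverse events of 17% at 400 mg/day and 8% at 200 mg/day (Section 2.5).

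- Lacosamide patients stopping for adverse events: 151 × 0.17 = 25.7, or 151 × 0.08 = 12.1.
- Lacosamide patients reaching one year: 151 × 0.92 × 0.85 × 0.83 = 98, or 109 with 0.92 in place of 0.83. Deaths and other removals are ignored, so these are high-side figures.

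**4. The plan's own power.** HR = ln(0.92)/ln(0.80) = 0.374, as stated. A log-rank simulation with N = 298, exponential times, censoring at one year and 15% lost uniformly over the year (10,000 runs) gives 83.4%, against the stated 83.6%. The design figure reproduces.

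**5. Sensitivity to withdrawal seizures (rates assumed).** N = 302, 17% of the lacosamide arm stopping at a uniform time in the year, 5,000 runs per case:

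| Assumed withdrawal-seizure risk per stopper | Lacosamide events | Power |
|---|---|---|
| 0% | 11.2 | 84% |
| 2% | 11.6 | 81% |
| 5% | 12.2 | 78% |
| 10% | 13.4 | 69% |

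With 8% stopping, a separate simulation (8,000 runs) gives 83.5, 81.5 and 79.0% at 0, 5 and 10%.

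For scale, the placebo risk over 14 days is 0.223 × 14/365 = 0.85%, where 0.223 = −ln(0.80). An assumed 2% is thus about 2.3 times, and 5% about 6 times, the placebo risk over two weeks.

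**6. Who enters the primary test.** One-year completers stop at the administrative censoring date, so a later seizure does not enter it. For early stoppers, the ITT rule in Section 11.2.1 keeps all data after first dosing, and the per-protocol rule keeps 30 days after discontinuation.

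**The case against.** Silence is not an instruction to stop abruptly. Section 10.1 lists grounds, not dosing steps. Section 6.3 lets the investigator go down to 50 mg bid and prompts thought about a lower dose. Leaving the schedule to clinicians matches how peri-operative AEDs are handled. This stands in part: a reader might infer that the plan orders an abrupt stop, and it does not. But permission during toxicity management is not a discontinuation rule, and it does not address completers or patients who withdraw.

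There are also safeguards. Patients are taught to report possible seizures at once (9.1). Adverse events count for 30 days after stopping (11.2.1, 11.2.5). A first convulsion is a listed example of a serious event (15.6). Unblinding may be requested at discontinuation (15.12), and lacosamide is commercially available (3.15). So capture is not absent. None of these requires a step-down or schedules a seizure contact after the one-year visit. The calendar's combined dispensing-and-return mark at the last visit, and resupply on request (15.3.2), leave room for taper drug but plan none.

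A reader might also infer that the design is seriously underpowered, or that the analysis wrongly penalises lacosamide. The documents support neither. The withdrawal-seizure rates are assumptions. The stopping rates come from patients with chronic epilepsy on 1 to 3 other AEDs, whereas this trial requires no seizure for at least 10 years (4.18). Counting an early stopper's seizure is what an ITT analysis should do.

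**Conclusion.** The point holds as an inexpensive improvement, mainly for patient safety. The protocol recognises a hazard and gives no step-down at one year, on voluntary withdrawal, or for toxicity above 50 mg bid. After the one-year visit no planned contact asks about seizures.

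The size of the harm cannot be derived from the documents. Power is unchanged if withdrawal causes no seizures, and is about 81% against 84% at an assumed 2% in 17% of the lacosamide arm. The lower figures above rest on risks several times the placebo hazard and should not be read as forecasts. Completers, the largest group, affect safety only.

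One limit remains. Some pages were not available, including those after the pill-count form in Appendix 17.4, where the patient education sheet would fall. Advice on stopping there cannot be excluded.

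**What to change.** Add to Sections 6.3 and 10.1: at one-year completion, and at early discontinuation where the patient agrees, lacosamide or placebo is stepped down blinded in both arms, for example by 100 mg/day each week. For completers, supply is dispensed at the last treatment visit. Except:

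- cases where the investigator judges that an immediate stop is needed (for example AV block or multi-organ hypersensitivity);
- pregnancy, at the investigator's judgment;
- patients who have had a seizure, who move to open-label AED treatment.

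Add one contact about 30 days after the last dose to record seizures, and report these by arm. State that seizures after the one-year censoring date do not enter the primary analysis and that early stoppers' seizures stay in the ITT analysis. As an editorial matter, let the toxicity ground in 10.1 point to 6.3 as well as 6.1.3.

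The cost is one amendment and a site notice. Per patient it is up to 56 tablets (28 × 100 mg + 28 × 50 mg = 4,200 mg = 7 × (300 + 200 + 100) mg), up to three more weeks of drug exposure, and one telephone call. No patients are added.

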11.0 STATISTICAL CONSIDERATIONS

11.1 Overview

The primary analysis for this study is a randomized, two-arm, parallel group, multicenter trial enrolling post-operative patients with newly-diagnosed high-grade glioma (HGG). Patients will be randomly assigned to either lacosamide (L) or placebo (P). Patients will be randomized to either treatment using a 1:1 randomization scheme. Based on a retrospective review of available data we assume a 20% seizure risk in the P group and 8% in the L group (after 1 year of observation). Based on these assumptions and assuming that time to first seizure follows an exponential distribution we estimate the hazard ratio between the L and P arms to be 0.374. Additional assumptions of the trial are that patients will be administratively censored after 1 year of follow-up and that 15% of patients will be lost to follow-up. The reason for the first assumption is that risk of seizure is greatest during the first year and as such clinical interest focuses on this time period. Because standard software packages do not incorporate administrative censoring we developed a SAS IML program to estimate the power associated with this clinical trial design.

Based on this simulation program, the maximum fixed sample size to be accrued is 298 patients. The power for this analysis is 83.6% (power based on 1000 simulations). Because we plan 1 interim analysis using an O'Brien-Fleming stopping rule, we will need to adjust the sample size upward using the group sequential-to-fixed sample size ratio of 1.008 [35]. While this ratio is exact for trials with 80% power, it is a conservative lower bound for trials with greater than 80% power [35]. This ratio results in a trial with 302 patients (i.e., the largest even integer greater than 298×1.008). This results in a trial with 151 patients randomized to L and 151 patients randomized to P. The primary measure of efficacy is time to first seizure (TFS). The primary test of the difference in TFS between the treatment arms will be based on the likelihood ratio statistic for the treatment effect in a stratified proportional hazards regression model with anticonvulsant use as the stratification factor. The MDACC DSMB will periodically meet (either once every 6 months or annually) to evaluate safety and efficacy. The interim analysis will take place after 21 events have been observed. We will assess efficacy using an O'Brien-Fleming stopping rule with a nominal critical value of 2.7959 at the interim analysis. A futility analysis based on a conditional power assessment may be performed if the hazard ratio between the two treatment arms is approximately 1. If a conditional power assessment is performed and the conditional power is less than 0.10 the trial will be stopped for futility. The decision to perform this futility analysis will include an assessment of the number of events observed (i.e., at least 50% of the expected 42 events have occurred and all patients have not yet enrolled in the trial). If the study continues to full accrual, the final analysis will take place when all of the patients have either been followed for 1 year or have experienced a seizure event. We will test the null hypothesis $HR=1.00$ against $HR \neq 1.00$ at the 0.05 level. The conditional power for the time-to-event outcome will be computed based on the method described in Design and Analysis of Clinical Trials with Time-to-Event Endpoints (Peace 2009, page 60) and Lan Simon and Halperin (1982).

Descriptive and inferential statistics will be used to summarize the treatment effects. The mean, standard deviation, median, 25% percentile, 75% percentile, minimum, and maximum will be reported for continuous variables by treatment group. For discrete (qualitative) outcomes, descriptive analyses will be based on the distribution of these discrete outcomes and will be reported as percentages and patient counts by treatment. Time to event endpoints will be descriptively summarized by Kaplan-Meier curves. Point and interval estimates of treatment effects will be based on maximum likelihood methods. For binomially distributed variables, we will report proportions, their 95% confidence intervals, differences in proportions and 95%

confidence intervals for the difference in proportions. Estimates of treatment effects for time to event endpoints will be based on the ratio of hazard functions (L: P) using Wald type scores from a Cox proportional hazards regression model. Unless stated otherwise, all statistical tests will be assessed using a two-sided $\alpha = 0.05$ significance level and confidence intervals will be constructed using two-sided 95% and will be based on the normal approximation. Although multiple secondary endpoints will be evaluated we will make no adjustment for multiplicities associated with these multiple tests.

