1.0 OBJECTIVES

- 1.1 **Study design:** This is a multicenter, randomized, placebo-controlled trial to assess the efficacy of prophylactic administration of the antiepileptic drug (AED) Lacosamide in patients with newly-diagnosed high-grade glioma (HGG).
- 1.2 **Primary objective:** The primary objective of this study is to determine if prophylactic administration of Lacosamide reduces the risk of seizures in patients with HGG. This will be tested in newly-diagnosed post-operative patients during the first year after tumor diagnosis. The primary endpoint will be time to first seizure.
- 1.3 **Secondary objectives:** The secondary objectives of this study are to determine the one-year risk of first seizure in this patient population and to evaluate patient reported symptoms.
- 1.4 **Exploratory objectives:** The exploratory objectives of this study are:
- To investigate clinical and electroencephalographic predictors of seizures in this patient population.
 - To evaluate the occurrence of symptoms and correlate to seizure activity as well as tolerance to treatment using the MD Anderson Symptom Inventory-Brain Tumor Module (MDASI-BT) self-reporting tool.

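### The expected 42 events leave out the plan's own 15% loss (about 39), and no rule for death before a first seizure supports the one-year risk estimate

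*Combined protocol and SAP*

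**What the plan says.** Section 1.3 sets the objective: "The secondary objectives of this study are to determine the one-year risk of first seizure in this patient population".

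Section 11.1 assumes one-year seizure risks of 20% on placebo and 8% on lacosamide with exponential times, from which "we estimate the hazard ratio between the L and P arms to be 0.374". It names two reasons for incomplete follow-up: "patients will be administratively censored after 1 year of follow-up and that 15% of patients will be lost to follow-up". The stated power is 83.6% at a fixed sample size of 298, raised to 302 (151 per arm) for one interim look.

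On timing, "The interim analysis will take place after 21 events have been observed", with "a nominal critical value of 2.7959 at the interim analysis". The optional futility look requires that "at least 50% of the expected 42 events have occurred". The final analysis waits until every patient has had either a year of follow-up or a seizure.

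For reporting, "Time to event endpoints will be descriptively summarized by Kaplan-Meier curves", with treatment effects as Cox hazard ratios. No estimator is tied to the one-year risk. In Section 11, death appears only in the safety listings of Section 11.2.5.

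**The concern.** Two gaps meet in the same section.

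First, the event count and the loss assumption stand close together but do not agree. The interim timing, its boundary and the futility condition all use 42 as the denominator.

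Second, patients with high-grade glioma may die without having had a seizure, and the protocol plans survival follow-up (Section 8.6). The efficacy text does not say whether such a death is censored or treated as a competing event. Read literally, a patient who dies seizure-free within the year never meets the final-analysis trigger. If deaths are censored, one minus Kaplan-Meier estimates the risk that would apply if nobody died. A reader would take it as the share of patients who will have a seizure within a year, and it is higher than that. At stake are the absolute one-year risks and their difference, and the information fraction at the interim.

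**Working it through.** **Inputs from Section 11.1:** risks 20% and 8%; exponential times; one-year censoring; 15% loss; 151 per arm; 21 interim events; boundary 2.7959. **Assumed:** timing of the loss; one-year mortality, equal in both arms and independent of seizure; a final critical value of 1.977, taken as 2.7959/√2.

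**1. The plan's own figures.** Hazards are −ln(0.80) = 0.2231 and −ln(0.92) = 0.0834. Their ratio is 0.374, as stated. Events with no loss: 151 × (0.20 + 0.08) = 42.3, which gives the stated 42.

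**2. Events with the 15% loss.** For loss at uniform times, the probability of an observed event is 0.85(1 − e^−λ) + 0.15[1 − (1 − e^−λ)/λ].
- Placebo: 0.170 + 0.0156 = 0.1856.
- Lacosamide: 0.068 + 0.0061 = 0.0741.
- Events: 151 × 0.2596 = 39.2. Exponential loss gives 39.1.
- If all loss falls at entry: 0.85 × 42.28 = 35.9.

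**3. Does the stated power include the loss?** Simulated power of the likelihood-ratio test at 298 patients (unstratified, 10,000 runs per case):

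| Loss | Power |
|---|---|
| None | 86.7% |
| Spread over the year (exponential / uniform) | 83.8% / 83.4% |
| All at entry | 80.3% |

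The stated 83.6% matches only loss spread over the year. The power figure therefore includes the loss and the event count does not.

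**4. Interim.** The information fraction is 21/39.2 = 0.536. The two-look O'Brien-Fleming boundary is 2.80 at 0.50 and 2.71 at 0.536. Using 2.7959 at 0.536 and 1.977 at the end gives a two-sided type I error of 0.0498. Half of 39.2 is 19.6 events, against 21 under the plan's count.

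**5. Risk faced when deaths occur.** With death hazard μ = −ln(1 − mortality), cumulative incidence is λ/(λ+μ) × (1 − e^−(λ+μ)). Example at 20% mortality: μ = 0.2231, so placebo is 0.5 × (1 − 0.64) = 18.0%. Reading 20% and 8% as death-free risks:

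| Assumed one-year mortality | Placebo | Lacosamide | Difference |
|---|---|---|---|
| 0 (equals one minus Kaplan-Meier) | 20.0% | 8.0% | 12.0 points |
| 10% | 19.0% | 7.6% | 11.4 |
| 20% | 18.0% | 7.2% | 10.8 |
| 30% | 16.9% | 6.7% | 10.2 |
| 40% | 15.8% | 6.3% | 9.5 |

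The overstatement of the difference is 0.6 to 2.5 points. The 95% half-width, 1.96 × √{[p₁(1−p₁) + p₂(1−p₂)]/151}, is 7.0 to 7.6 points over the 10% to 40% rows. The risk ratio stays between 2.50 and 2.51.

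**6. A simple proportion instead.** With no deaths and uniform loss, counting the lost as seizure-free gives 18.6% and 7.4%. Excluding them gives 0.1856/(1 − 0.1344) = 21.4% and 0.0741/(1 − 0.1439) = 8.7%. Neither returns 20% and 8%.

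**The case against.** The strongest reply is that little depends on either gap. The final analysis is triggered by follow-up, not by an event count. The boundary error is on the strict side. The futility look is discretionary and asks for at least half of the events, which 21 of 39 satisfies. All of this stands. A reader might infer from the wrong 42 that the trial is underpowered or that its error rate is inflated. Steps 3 and 4 support neither. The figure of 39 itself depends on when patients are lost, which the plan does not state, although the power check points to loss spread over the year.

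A second reply is that the risks in step 5 rest on an unstated reading. Section 11.1 takes 20% and 8% from a retrospective review and does not say whether deaths were already in the denominator. If they were, the risk patients face is 20% and 8% as stated, and one minus Kaplan-Meier on placebo would be about 22%, 24% and 25% at 20%, 30% and 40% mortality. This stands too. The direction of the bias is the same on both readings, but the printed risks are conditional.

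A third reply is that the plan may not intend Kaplan-Meier for the one-year risk at all: "For binomially distributed variables, we will report proportions, their 95% confidence intervals". That is possible, since the plan names Kaplan-Meier only for descriptive curves. But a proportion needs a rule for the lost patients, and the plan gives none (step 6).

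It is also tempting to say that deaths cut the power. If deaths of 20%, 30% or 40% came on top of the 15% loss, simulated power at 302 would be roughly 80%, 77% and 75%. If the 15% consists of deaths, about 39 events and roughly the stated power remain. The documents do not say which applies.

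**Conclusion.** Both parts hold, at modest size.

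The figure of 42 is wrong on the plan's own inputs. It should be about 39 with loss spread over the year, or about 36 if all loss falls at entry. The interim is then at about 54% information, where the matching boundary is about 2.71. Type I error is essentially intact (given an assumed final critical value of 1.977), and neither the 83.6% power nor the sample size of 302 is overturned.

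The efficacy text has no rule for death before a first seizure. With deaths censored, one minus Kaplan-Meier overstates the one-year risk patients face at any non-zero mortality. The amount cannot be fixed from the documents; the table in step 5 rests on assumed mortality and on 20% and 8% being death-free risks. Even at 40% mortality the effect on the difference is smaller than its sampling error, but it is systematic.

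A reader might infer that the primary test is biased. It is not: a Cox comparison with deaths censored is a valid cause-specific comparison, and the primary conclusion is unaffected. Power falls below the stated figure only if deaths exceed the 15% loss or come on top of it.

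**What to change.** In Section 11.1, with no change in sample size:

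1. Restate expected events as about 39, give the loss-timing assumption, and align the interim information fraction, boundary and 50% futility condition with it.
2. Estimate the one-year risk of first seizure per arm, and the difference with a 95% confidence interval, by Aalen-Johansen cumulative incidence with death as a competing event and loss to follow-up censored. Where seizure status before death is unknown, censor at the last seizure assessment.
3. State that the stratified Cox likelihood-ratio test censors deaths.
4. Add death to the final-analysis trigger.
5. State whether the 15% includes deaths.

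The cost is wording and a rerun of the existing power program. Survival follow-up is already planned, though only where possible (Section 8.6). One limit remains: Section 8.4 does not say whether the monthly seizure call continues after treatment stops, and the Figure 8-1 footnote ties the four-weekly symptom and adverse-event calls to the treatment period. If many deaths follow an unobserved interval, the last-assessment rule will be used often and will move the estimate back towards Kaplan-Meier, so its frequency should be reported by arm. The downside is that the stated event count and absolute risks become slightly less favourable.
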